**Study end-points:**

***Primary end-point***

- i. Time to vasopressor independence. Defined as the time from starting the active treatment/placebo to discontinuation of all pressors
- ii. Delta SOFA score, defined as the initial SOFA score minus the day 4 SOFA score

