**Power Calculation:**

Based on the results of the preliminary study of Marik et al we project that the combination of hydrocortisone, vitamin C and thiamine could reduce time to vasopressor discontinuation from 54 (+/- 30 hours) versus 30 hours. For the additional primary outcome we projected a greater change of SOFA score of 4 (+/- 3) versus 2. Assuming a type 1 error of 5% (alpha of 0.05) and a power of 80% (the ability to detect a difference between two groups when a difference exists) would require a sample size of 94 patients. To account for dropouts and patients not requiring vasopressor therapy we will therefore aim for a sample size of 140 patients.

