***Data Collection:***

The following de-identified demographic and clinical data will be collected.

- i. Age
- ii. Sex
- iii. Weight
- iv. Admitting diagnosis and possible site of infection
- v. Blood culture results
- vi. Co-morbidities, including diabetes, hypertension, cardiac failure, COPD, malignancy
- vii. Requirement for mechanical ventilation (Y/N).
- viii. Use of vasopressor agents (Y/N). The hourly dosage of vasopressors will be recorded as the norepinephrine equivalent dosage. [70,71]
- ix. Duration of vasopressor use
- x. Time to vasopressor independence from start of active drug/placebo
- xi. Daily urine output (for first 4 days)

xii. Fluid balance after 24 and 72 hours

xiii. Presence of acute kidney injury (AKI). Presence of AKI: Acute kidney injury (AKI) will be defined using the KDIGO criteria; namely, an increase of the s-creatinine > 0.3 mg/dl or a level > 1.5 times the baseline value. [27] If the baseline s-creatinine is not known a value > 1.5 mg/dl will be regarded as diagnostic of AKI.

xiv. Length of ICU and hospital stay

xv. ICU, hospital, and 28-day mortality

xvi. Routine laboratory data for 4 days including:

a. serum creatinine

b. white cell count (WBC)

c. platelet count

d. total bilirubin

e. PaO2/FiO2 ratio

f. Procalcitonin (PCT) – on days 1 and 4

g. lactate level

h. urine oxalate level (day 4)

xvii. HostDx Sepsis genetic testing (day 1) if consent is provided for additional sub-study.

xviii. The patients' admission APACHE II and APACHE IV scores will be recorded. The APACHE IV score allows calculation of the predicted hospital mortality and predicted ICU length of stay (LOS).

ix. The daily SOFA (Sepsis-related Organ Failure Assessment) score will be recorded for the first 4 treatment days.

The APACHE II score (incrementing score of 0-71) and APACHE IV score (incrementing score 0-286) are standardized measures of disease severity that are used to predict hospital mortality and ICU LOS.

[72,73] The SOFA score was designed to sequentially assess the severity of organ dysfunction in patients who are critically ill from sepsis (incrementing score 0-24). [74]. The SOFA scores is calculated 24 hours

after admission to the ICU and daily thereafter. SOFA scores that increase by about 30 percent are associated with a mortality of at least 50 percent.[75]

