***Data analysis:***

Summary statistics will be used to describe the clinical data and presented as mean  $\pm$  SD, median with interquartile range (IQR) or percentages as appropriate. Chi squared analysis with Fisher’s exact test (when appropriate) and Student’s t test (Mann Whiney U test for non- normal distributions) were used to compare data between the active treatment group and the placebo group with statistical significance declared for probability values of 0.05 or less.

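### Delta SOFA is compared between arms without adjusting for the initial score; the planned test is valid, but adjustment set in advance would be more precise and guard against chance imbalance

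*Protocol*

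**What the plan says.** The Protocol (Study end-points, Primary end-point ii) defines the measure as "Delta SOFA score, defined as the initial SOFA score minus the day 4 SOFA score", and the SAP repeats it. Under Power Calculation the plan states: "For the additional primary outcome we projected a greater change of SOFA score of 4 (+/- 3) versus 2". Under Data analysis, continuous outcomes get Student's "t test (Mann Whiney U test for non- normal distributions) were used to compare data between the active treatment group and the placebo group". Neither document names a covariate, a regression model or any baseline adjustment. The propensity adjustment in the Protocol's background belongs to the earlier retrospective study, not to this trial.

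Data Collection gives the SOFA range ("incrementing score 0-24") and has the score recorded on each of the first four treatment days, so both scores needed for adjustment are planned. The same section times the score at 24 hours after ICU admission and daily from then on. The inclusion criteria admit sepsis as well as septic shock, diagnosed within 12 hours of ICU admission, and neither the inclusion nor the exclusion criteria set a minimum SOFA. Allocation comes from a random number table; no stratification by severity is described.

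**The concern.** Subtracting the initial score is not the same as adjusting for it. Subtraction removes a baseline difference between the arms completely only if day-4 SOFA rises one point for each point of initial SOFA. If the slope is below 1, as regression toward the mean would usually make it, the arm that happens to start sicker shows the larger fall without any treatment effect. Initial scores are likely to vary widely, because entry covers sepsis with and without shock.

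Two things are at stake on a primary end-point whose whole projected effect is 2 points. One is precision: the raw change does not make full use of two scores already in hand. The other is credibility: if a visible imbalance in initial SOFA occurs, an adjustment added afterwards would look driven by the data, whereas one named in advance would not.

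**Working it through.** **Inputs from the documents.** Difference 4 − 2 = 2 points, with 3 read as the SD of the change; alpha 0.05 and 80% power; 94 patients, raised to 140 (Power Calculation). **Assumed, because not stated:** two-sided test; equal arms (47 or 70 each); correlation r between initial and day-4 SOFA of 0.3, 0.5 or 0.7; ratio k of the day-4 SD to the initial SD, first k = 1.

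**The plan's own figure.** With a 2-point difference, SD 3, two-sided alpha 0.05 and 80% power, the t-test calculation gives 74 patients in total. The vasopressor end-point (54 versus 30 hours, SD 30) gives 52. Neither gives 94. That is a separate matter; here it means only that 94 exceeds what delta SOFA needs on the stated inputs.

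**How much imbalance passes through.** Let day-4 SOFA have slope b on initial SOFA, with b = r·k. Then

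difference in mean delta = treatment effect + (1 − b) × difference in mean initial SOFA.

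With k = 1, b = r. Each 1-point imbalance moves the comparison by 0.7, 0.5 or 0.3 points at r = 0.3, 0.5, 0.7, that is 35%, 25% or 15% of the projected effect.

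A typical imbalance follows from the SD of the change: 3 = s√(2(1 − r)), so s = 2.54, 3.00 or 3.87. With 47 per arm the standard error of the baseline difference is s√(2/47) = 0.52, 0.62 or 0.80. A one-standard-error imbalance then moves delta SOFA by 0.37, 0.31 or 0.24 points. The standard error of the delta comparison itself is 3√(2/47) = 0.62, and this variation is already part of it.

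**Validity.** In 20,000 simulated null trials (normal scores, r = 0.5, SD 3, 47 per arm) the unadjusted t test rejected in 5.1% overall. Among trials whose imbalance was 0.8 to 1.2 points it rejected in 8.3%.

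**Precision.** With k = 1, Var(change) = 2s²(1 − r) and Var(adjusted) = s²(1 − r²). The ratio is (1 + r)/2 = 0.65, 0.75 or 0.85. The SD of 3 becomes 3√((1 + r)/2) = 2.42, 2.60 or 2.77, and confidence intervals are 19% to 8% narrower.

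**Power** (two-sided t test, using the adjusted SD):

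| True difference | N | Unadjusted | r = 0.3 | r = 0.5 | r = 0.7 |
|---|---|---|---|---|---|
| 2 points (the plan's) | 94 | 89% | 98% | 96% | 93% |
| 2 points (the plan's) | 140 | 97.5% | 99.8% | 99.5% | 98.9% |
| 1.5 points (assumed) | 94 | 67% | 84% | 79% | 74% |
| 1.5 points (assumed) | 140 | 84% | 95% | 92% | 89% |

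**Unequal SDs.** In general the variance ratio is k²(1 − r²)/(1 + k² − 2rk). For r = 0.3, 0.5, 0.7:

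- k = 0.8: 0.50, 0.57, 0.63
- k = 1.2: 0.76, 0.87, 0.97
- k = 1.5: 0.87, 0.96, 0.998

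**The case against.** The strongest reply is that the planned test is sound. Under randomisation the raw change score is unbiased, its overall type I error is held, and chance imbalance is already counted in its standard error. All of that stands. A reader might infer that the planned comparison is biased or invalid; the documents do not support that.

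A reader might also infer that the trial is underpowered for delta SOFA. On the plan's own inputs it has 89% power at 94 patients without adjustment. Part of the increase to 140 covers patients who need no vasopressors, and they still contribute a delta SOFA. The evaluable number should therefore lie above 94, where adjustment adds less.

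The size of the gain rests on r and two SDs that the documents do not give, and under some patterns it is close to nothing. This stands too, and is why ranges are shown.

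The floor of the scale is another tempting argument: a patient entering at SOFA 3 cannot improve by 4. But 4 is a projected group mean, not a threshold for each patient, and linear ANCOVA does not remove the floor. It is not the basis of this point.

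Finally, a random number table does not show whether the sequence was blocked, so nothing here depends on calling the randomisation simple.

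**Conclusion.** The point holds as a matter of efficiency and robustness, not as a flaw that invalidates the end-point. Delta SOFA would be tested without using the initial score as a covariate. This usually costs precision and leaves the result exposed to whatever imbalance occurs.

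With equal SDs and r from 0.3 to 0.7, the unadjusted estimate has 1.54 to 1.18 times the variance of the adjusted one (1/0.65 to 1/0.85), and 70% to 30% of any imbalance passes through, not all of it. The gain in power is modest if the 2-point effect is real. It is largest if the true effect is smaller or fewer day-4 scores are available. The variance ratio could be as low as 0.50 or as high as 0.998 over the SD patterns examined. The change is worth making before unblinding because it costs little and cannot be made credibly afterwards.

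**What to change.** In the SAP, and in the Protocol's Data analysis section:

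1. Name the primary comparison of delta SOFA as ANCOVA of day-4 SOFA on treatment, with initial SOFA as covariate. Using delta SOFA as the response gives the same treatment estimate, apart from its sign. Report the adjusted mean difference with its 95% CI, and the raw deltas descriptively.
2. Define initial SOFA as the last score from data obtained before the first study dose. With diagnosis allowed within 12 hours of ICU admission and the score timed at 24 hours after it, the recorded initial score could follow treatment. The raw delta has the same weakness.
3. For marked non-normality, specify robust standard errors or a rank-based ANCOVA as the sensitivity analysis, in place of the unadjusted Mann-Whitney test.

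Any rule adopted for patients without a day-4 score applies unchanged.

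The cost is a few sentences, slightly more analysis work and, where needed, abstraction of the pre-dose score; no extra patients or visits. The downside is a linearity assumption that the floor at 0 may strain.

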***Secondary end-points***

- iii. 28-day mortality
- iv. Hospital mortality
- v. PCT clearance (PCT-c) calculated using the following formula: initial PCT minus PCT at 96 hours, divided by the initial PCT multiplied by 100. [67,68]
- vi. ICU mortality
- vii. ICU length of stay (LOS) and ICU free days. ICU free days is calculated as the number of days alive and out of the ICU to day 28
- viii. Hospital LOS

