## **Vitamin C, Hydrocortisone and Thiamine dosing protocol and randomization**

### ***Medication dosing.***

Based on published clinical data, vitamin C pharmacokinetic modeling, the package insert as well as the preliminary study by Marik et al, Vitamin C will be administered as an intravenous dose of 6gm per day divided in 4 equal doses. [22-24,34-37] This dosage is reported to be devoid of any complications or side effects. Hydrocortisone will be dosed according to the consensus guidelines of the American College of Critical Care Medicine.[52] Thiamine will be administered according to current recommendations in a dose of 200mg q 12 hourly. [69]

This is a double-blind placebo controlled study. Only the dispensing pharmacist will be aware of the treatment allocation. Patients will be randomized to receive either vitamin C/hydrocortisone/thiamine or triple placebo using a random number table provided to the dispensing pharmacists. Each patient will be allocated a unique subject ID which will be linked to the randomization sequence. Only the dispensing pharmacists will have a record of the subject ID and randomization sequence. The vitamin C, vitamin C-placebo, hydrocortisone, hydrocortisone-placebo, thiamine, and thiamine-placebo will be formulated as follows:

***Vitamin C:*** Vitamin C is provided by the manufacturer as a 50 ml vial at a concentration of 500mg/ml. Three (3) ml of vitamin C will be placed in a 50 ml bag of Normal Saline (1500 mg vitamin C in 50ml bag) which will then be infused over 30 minutes (100mL/hr). The bag will be labeled by the pharmacy as “Vitamin C 1.5g or Placebo”. The dosing schedule is 1500mg every 6 hours for 4 days (or discontinued earlier if discharged from the ICU).

Once the vial is open, it is only stable for 6 hours. The resulting product is given 12 hour stability. When first ordered, 2 doses are made then and sent to the nurse. For next 12 hours, they will wait until 1 hour prior to make the next batch.

Vitamin C placebo will consist of an identical bag of 50mL normal saline (but with no vitamin C) and will be labeled “Vitamin C or Placebo”. Placebo will be infused over 30 minutes as per the infusion instructions of the active vitamin.

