Outcomes of Metabolic Resuscitation Using Ascorbic Acid, Thiamine, and Glucocorticoids in the Early Treatment of Sepsis.

ORANGES Trial

NCT#: NCT03422159

Document Date: May 13th, 2019

Study end-points:

Primary end-point

- i. Time to vasopressor independence. Defined as the time from starting the active treatment/placebo to discontinuation of all pressors
- ii. Delta SOFA score, defined as the initial SOFA score minus the day 4 SOFA score

Secondary end-points

- iii. 28-day mortality
- iv. Hospital mortality
- v. PCT clearance (PCT-c) calculated using the following formula: initial PCT minus PCT at 96 hours, divided by the initial PCT multiplied by 100. [67,68]
- vi. ICU mortality
- vii. ICU length of stay (LOS) and ICU free days. ICU free days is calculated as the number of days alive and out of the ICU to day 28
- viii. Hospital LOS

Power Calculation:

Based on the results of the preliminary study of Marik et al we project that the combination of hydrocortisone, vitamin C and thiamine could reduce time to vasopressor discontinuation from 54 (+/- 30 hours) versus 30 hours. For the additional primary outcome we projected a greater change of SOFA

score of 4 (+/- 3) versus 2. Assuming a type 1 error of 5% (alpha of 0.05) and a power of 80% (the ability to detect a difference between two groups when a difference exists) would require a sample size of 94 patients. To account for dropouts and patients not requiring vasopressor therapy we will therefore aim for a sample size of 140 patients.

Data analysis:

Summary statistics will be used to describe the clinical data and presented as mean \pm SD, median with interquartile range (IQR) or percentages as appropriate. Chi squared analysis with Fisher's exact test (when appropriate) and Student's t test (Mann Whiney U test for non- normal distributions) were used to compare data between the active treatment group and the placebo group with statistical significance declared for probability values of 0.05 or less.

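### PCT clearance is defined at 96 hours but PCT is drawn on days 1 and 4 with no time zero or window, and neither planned test adjusts for initial PCT

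*Protocol*

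**What the plan says.** Secondary end-point v defines clearance as "initial PCT minus PCT at 96 hours, divided by the initial PCT multiplied by 100". The SAP repeats it ("initial PCT minus PCT at 96 hours"). Neither says what the 96 hours are counted from or what makes a value the initial one.

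The protocol's Data Collection section lists PCT on days 1 and 4, under the heading "Routine laboratory data for 4 days including". It gives no draw hour, window or day-numbering rule. The nearest clock is the treatment course: "The dosing schedule is 1500mg every 6 hours for 4 days (or discontinued earlier if discharged from the ICU". Other items use other clocks. Time to vasopressor independence runs from the start of study treatment, and SOFA is first calculated 24 hours after ICU admission.

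Data analysis offers Student's "t test (Mann Whiney U test for non- normal distributions) were used to compare data between the active treatment group and the placebo group", and the SAP has the same text. Summaries may be mean with SD or "median with interquartile range (IQR) or percentages as appropriate". No model adjusts for a baseline value, no log transform is mentioned, and no rule covers a missing second PCT. Among the non-mortality end-points, only ICU-free days builds in death: "ICU free days is calculated as the number of days alive and out of the ICU to day 28".

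**The concern.** Two readers could apply the definition and the schedule differently and both be within the text. One draws the second sample at the end of the four-day course. The other draws it with the day-4 morning bloods. Their clearance values would then not be measured at the same time, and neither would be clearly wrong. If the initial value is only a day-1 value, it could also be taken after the first dose.

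The second issue is efficiency. Percent clearance cannot exceed 100 but has no lower limit, and initial PCT enters only as the divisor. The trial already collects the initial value, and using it as a covariate would usually give a more precise comparison. What is at stake is the interpretation and precision of one secondary end-point.

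**Working it through.** The plan gives no effect size, SD, half-life or power for PCT, so there is no stated figure to reproduce. Every PCT input below is an assumption.

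**1. Clock.** If day 1 is hours 0 to 24, day 4 is hours 72 to 96.
- A draw at the close of day 4 is at 96 h and satisfies both statements.
- A draw at the same clock hour as day 1 is at 3 × 24 = 72 h.
- If days are calendar days, the gap between the two samples can run from just over 48 h to just under 96 h.

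**2. Effect of draw time.** Assume exponential decline with half-life *h*, so clearance at time *t* is 100 × (1 − 0.5^(t/h)).

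| h | 72 h | 96 h | Remaining PCT, 72 h ÷ 96 h = 2^(24/h) |
|---|---|---|---|
| 24 h | 87.5% | 93.8% | 2.00 |
| 36 h | 75.0% | 84.3% | 1.59 |
| 48 h | 64.6% | 75.0% | 1.41 |

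The level moves by about 6 to 10 points. For the added noise, suppose draws are spread evenly over 72 to 96 h. The SD of draw time is 24/√12 = 6.93 h, and the added SD of log PCT is 6.93 × ln 2/h, which is 0.20 (h = 24) or 0.13 (h = 36). Against an assumed between-patient log-SD of 1.0, the total is √(1 + 0.20²) = 1.02 or √(1 + 0.13²) = 1.01. If half the patients are drawn at exactly 72 h and half at 96 h, the SD of draw time is 12 h. The added SD is then 0.35 (h = 24) and the total is 1.06.

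**3. Scale and choice of test.** A PCT rising from 0.5 to 5 gives (0.5 − 5)/0.5 × 100 = −900%. Simulation used 70 per arm (140 split equally, an assumption), a log-normal ratio of second to initial PCT with median 0.25 under placebo, and a 35% lower ratio under active treatment:

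| Log-SD of ratio | t test on clearance | Mann-Whitney | t test on log ratio |
|---|---|---|---|
| 0.8 | 0.79 | 0.89 | 0.90 |
| 1.0 | 0.54 | 0.71 | 0.72 |
| 1.3 | 0.28 | 0.48 | 0.50 |

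Skew costs the t test a good deal. Mann-Whitney recovers nearly all of it.

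**4. Using initial PCT as a covariate.** Assume a log-SD of 1.3 at each time, correlation ρ between log initial and log second PCT, 70 per arm and 35% lower PCT (ln 0.65 = −0.431).
- SD of the log ratio: 1.3 × √(2(1 − ρ)), which is 1.424 at ρ = 0.4 and 0.822 at ρ = 0.8.
- Residual SD after adjustment: 1.3 × √(1 − ρ²), which is 1.191 and 0.780.
- Variance ratio, adjusted to log ratio: (1 + ρ)/2, which is 0.70 and 0.90.
- z = 0.431/(SD × √(2/70)). Adjusted: 2.14 and 3.27. Log ratio: 1.79 and 3.10.
- Power ≈ Φ(z − 1.96). Adjusted: 0.57 and 0.90. Log ratio: 0.43 and 0.87.

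Simulation agrees: 0.56 to 0.90 for the adjusted log analysis, against 0.40 to 0.85 for Mann-Whitney on percent clearance.

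**The case against.** The strongest reply is that four days of treatment are 96 hours, so a day-4 draw can be the 96-hour value. That stands. A reader might infer that the 96-hour value is never collected, or that the end-point cannot be computed. The documents do not support either inference: the fault is an unresolved ambiguity.

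A reader might also set the 1.4- to 2-fold difference in remaining PCT beside a treatment effect of similar size. The two are not comparable. The first is the largest shift for one patient. In a blinded trial with one schedule, draw time is unrelated to arm, and step 2 shows that the added variance is small.

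On skew, the plan already allows Mann-Whitney and median with IQR, so skew is not an unhandled defect. What remains is that no criterion is given for choosing between the two tests.

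It is tempting to call the end-point survivor-only. That is an inference from silence: nothing says that deaths are excluded, and ICU discharge and missed samples are equally uncovered. An extreme scenario shows the scale. Assume no true PCT effect, a log-SD of 1.0 for the ratio, and early deaths that are always the patients with the worst ratios. Early deaths of 10% on placebo and 5% on active give median clearance of 77.9% vs 76.5% and means of 72.0% vs 67.8%. At 15% vs 5%, the medians are 79.3% vs 76.5% and the means 75.0% vs 67.8%. The artefact runs against the arm with fewer deaths. The documents give no early-death rates, and mortality is reported separately. Ranking deaths last would turn a biomarker end-point into a composite with mortality, which is debatable.

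Finally, clearance already scales each patient to the initial value, and the plan cites sources for the measure. Both are fair, and they are reasons to keep clearance as a description. Scaling is not covariate adjustment, as step 4 shows.

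**Conclusion.** The point holds in limited form. The definition and the sampling schedule need to be reconciled, because the text allows a second draw at 96 h or about 24 h earlier. The consequence is a shift in level of about 6 to 10 points (half-lives of 24 to 48 h assumed) and a small increase in variance, with no bias between arms.

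Separately, both planned tests leave out a covariate that the trial already collects. Adjusting for log initial PCT raises power from 0.40 to 0.56 at correlation 0.4 and from 0.85 to 0.90 at correlation 0.8, compared with Mann-Whitney, under the assumptions in step 4. The gain shrinks as the correlation rises and depends on variability and correlation that the documents do not give. PCT clearance is one of several secondary end-points and has no power claim, so this is a minor improvement.

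**What to change.** In the protocol's end-point definition, its Data Collection list and the SAP:

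- State one time point for the second PCT, counted from first dose, with a window.
- Define the initial PCT as the last value before first dose.
- Make the between-arm comparison log PCT at that time, adjusted for log initial PCT, and report it as a ratio of geometric means with a confidence interval. Keep percent clearance as a descriptive figure.
- Report, by arm, the number without a second PCT because of death, and separately the number missing for ICU discharge or a missed sample. A rank analysis placing deaths last can be an optional sensitivity analysis.

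The cost is a wording change, a slightly different model, and a less familiar summary for one unpowered secondary end-point. No extra samples are needed if the day-4 draw is kept.
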